11.1. Primary endpoint

Proportion of subjects with AEs, judged to be probably or definitely related to the IP within 90 days after the 1st IP.

The number and percentage of subjects with AEs, judged to be probably or definitely related to the IP within 90 days after the 1st IP will be presented by treatment group on the Safety population. The difference of the proportions between the treatment groups with the corresponding exact 95% Clopper Pearson CIs will be presented.

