Statistical Methods and Planned Analyses:	
Study populations
 

Enrolled Population: all individuals who sign the informed consent form. The Enrolled Population will be used for all subject disposition analyses.

Intent-to-Treat (ITT) Population: all subjects who are randomized, irrespective of any deviation from the protocol or premature discontinuation. The treatment group assignment will be designated according to initial randomization. The ITT population will serve as the primary basis for the analysis of efficacy. [REDACTED]

Per-Protocol (PP) Population: all ITT subjects who are treated and complete study procedures through Day 30 without a major protocol deviation potentially impacting efficacy measurement [REDACTED]. The PP population will be used as supportive basis for analysis of efficacy [REDACTED].

Completers Population: all ITT subjects who are treated and complete study procedures through Day 90 without a major protocol deviation potentially impacting efficacy measurement [REDACTED]. The Completers population will be used as supportive basis for analysis of efficacy, [REDACTED].

Safety Population: all randomized subjects who receive at least 1 dose of IP. The treatment group assignment in this population will be defined by the treatment actually received. This population will be used for the analysis of safety.

 
Primary endpoint analysis
 
Proportion of subjects with AEs, judged to be probably or definitely related to the IP within 90 days after the 1st IP administration:
 
The number and percentage of subjects with AEs, judged to be probably or definitely related to the IP within 90 days after the 1st IP will be presented by treatment group. The difference of the proportions between the treatment groups with the corresponding exact 95% Clopper Pearson confidence intervals (CIs) will be presented. [REDACTED]
 
Secondary endpoint analyses
 
The analyses of all efficacy and imaging endpoints will be performed on the ITT population as the main analysis and will be repeated on the PP and Completers populations as supportive analysis. Efficacy endpoints will be summarized and statistically compared between the treatment groups in the subgroups of the variables used for randomization stratification, also. [REDACTED]
 
Proportion of subjects with independent functional outcome and excellent functional outcome [REDACTED] after the 1st IP:
 
The number and percentage of subjects who achieve a score of 0 to 2 on the mRS [REDACTED] will be presented by treatment group. The number and percentage of subjects [REDACTED]

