### **8.3 Study Withdrawal, Removal, and Replacement of Subjects**

If a subject discontinues study treatment and is withdrawn from the study for any reason, the study site must immediately notify the Medical Monitor (see contact details in [Section 12.7.3](#)). The date and the reason for study discontinuation must be recorded on the electronic case report form (eCRF). Subjects who discontinue early from the study will be asked to complete all assessments listed at Visit 6 as indicated in the Schedule of Assessments ([Table 1](#)).

In the event that a subject discontinues prematurely from the study because of a AE or serious AE, the AE or serious AE will be followed up until it resolves (returns to normal or baseline values) or stabilizes, or until it is judged by the Investigator to no longer be clinically significant.

Once a subject is withdrawn from the study, the subject may not reenter the study.

A subject may voluntarily withdraw or be withdrawn from the study at any time for reasons including, but not limited to, the following:

- unacceptable toxicity or AE

- subject withdrawal of consent: at any time, a subject's participation in the study may be terminated at his/her request or on the basis of the Investigator's clinical judgment. The reason for subject withdrawal will be noted on the eCRF.
- intercurrent illness: a condition, injury, or disease unrelated to the primary diagnosis that became apparent during treatment and necessitated the subject's termination from the study
- general or specific changes in the subject's condition that renders him/her ineligible for further treatment according to the inclusion/exclusion criteria
- subject fails to adhere to the protocol requirements (e.g., drug noncompliance, failure to make the return visits in the Follow-Up Period)
- lost to follow-up: the subject stopped coming for visits, and study personnel were unable to contact the subject 3 times
- pregnancy, as indicated in [Section 12.7.5](#).

Additionally, the Sponsor may stop the study at any time for safety, regulatory, legal, or other reasons aligned with good clinical practice (GCP). This study may be terminated at the discretion of the Sponsor or any regulatory agency. An Investigator may elect to discontinue or stop the study at his or her study site for any reason, including safety or low enrollment.

Randomized but not treated subjects will not be replaced.

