## 13 STATISTICAL ANALYSIS

[figure not shown]
A SAP will be prepared after the protocol is approved. This document will provide further details regarding the definition of analysis variables and analysis methodology to address all study objectives. The SAP will serve as a compliment to the protocol and supersedes it in case of differences.

The statistical evaluation will be performed using SAS® software version 9.4 or higher (SAS Institute, Cary, NC). All data will be listed, and summary tables will be provided. Summary statistics will be presented by treatment group and overall (wherever applicable). For continuous variables, data will be summarized with the number of subjects (n), mean, standard deviation, median, minimum, and maximum by treatment group. For categorical variables, data will be tabulated with the number and proportion of subjects for each category by treatment group.

Further details of statistical analyses including relevant SAS code will be presented in the SAP.

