8.1. General Methods

- Analysis will be carried out using SAS® (version 9.4 or newer, SAS Institute Inc., Cary, NC). Templates for the summary tables, figures and subject data listings will be available separately.
- Data listings will include all data recorded for all enrolled and ITT subjects. Data will further be categorized by treatment group.
- Summary statistics will be presented by treatment group and overall (wherever applicable). For continuous variables, data will be summarized with the number of subjects (n), mean, standard deviation, median, minimum, and maximum by treatment group. For categorical variables, data will be tabulated with the number and proportion of subjects for each category by treatment group.
- This is an exploratory study, i.e., all statistical comparison between the treatment groups is not confirmatory but of descriptive nature. Where appropriate, descriptive statistics may be presented with 95% confidence intervals (CIs).
- The minimum and maximum will be reported with the same degree of precision (i.e., the same number of decimal places) as the recorded data. Measures of location (e.g., mean and median) will be reported to 1 degree of precision more than the recorded data, and measures of spread (e.g., standard deviation) will be reported to 2 degrees of precision more than the recorded data.
- The dictionary (MedDRA and WHO Drug) version used will be specified in corresponding data display footnote.
- Only data from protocol scheduled visits will be included in the summary tables. Data from unscheduled visits will not be included in summary tables but will be included in the listings.
- Any changes to the analyses that are not included in this SAP will be documented in the CSR.

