9.6. Study Drug Exposure

The total number of subject dosed, cumulative dose number, cumulative dose administered, planned cumulative dose (mg), relative dose intensity (%), relative dose intensity category and subject with at least one interrupted infusion, will be summarized descriptively for all subjects in safety population by treatment group. Also, all study drug administration data will be listed by subject.

This document is confidential.

10. Efficacy

All efficacy endpoints will be summarized and analyzed using the ITT population. Additionally, supportive analyses will be performed on the PP population and on the Completers population. Comprehensive listings of all efficacy data will also be presented by subject and visit.

All efficacy endpoints will be summarized using descriptive statistics by treatment group and by visit, as appropriate. Categorical endpoints will be summarized by treatment group by presenting the number and percentage of subjects in each category.

This is an exploratory study, i.e., all statistical comparison between the treatment groups is not of confirmatory but of descriptive nature. The statistical comparison of the efficacy endpoints based on mRS and NIHSS between treatment groups will be performed either after multiple imputation (MI) of missing data or will be analyzed

For all other efficacy endpoints missing data will not be imputed prior statistical comparison, i.e. summaries and statistical analysis will use the observed data within ITT only.

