10.1. Efficacy Endpoints for mRS and NIHSS and Analysis

10.1.1. Analysis of functional outcome based on mRS assessments

All binary response variables defined on mRS assessments at the respective visits will be summarized with the number and percentage of subjects with and without response by treatment group considering observed data of ITT. The difference of the proportions based on observed data of ITT between the treatment groups with the corresponding 95% confidence intervals (CIs) will be presented for the defined time points.

Comparison between the treatment groups will be performed for the binary response variables using the Chi-square test at each defined timepoint separately and additionally

Additionally, the comparison between the treatment groups at each timepoint and overall will be performed for the binary response

The model will be performed for both categorizations of mRS, i.e., subjects with mRS ≤ 2 and subjects with mRS ≤ 1

This document is confidential.

The number and percentage of subjects in each score category of mRS will be presented for baseline and for the post-baseline time points [REDACTED] by treatment group for observed ITT population. A shift table will be presented by treatment with shifts from baseline to each defined post-baseline time point [REDACTED]

[REDACTED]

The [REDACTED] steps are described in section 10.1.3.

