10.2. Further Efficacy Endpoints and Analysis

10.2.1 Occurrence of recurrent stroke within 90 days after the 1st IP:

The number and percentage of subjects who have a recurrent stroke within 90 days after the 1st IP will be presented by treatment group on the observed ITT. The difference of the proportions between the treatment groups with the corresponding 95% CIs will be presented.

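### The primary endpoint's between-group difference is given Clopper-Pearson limits, a one-sample method; SAP 11.1 should name a two-sample interval

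*SAP*

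**What the plan says.** SAP 11.1 has the number and percentage of subjects with the primary event presented by treatment group on the Safety population, and continues: "The difference of the proportions between the treatment groups with the corresponding exact 95% Clopper Pearson CIs will be presented". Protocol 13.4.1 uses the same sentence. The protocol synopsis, under its primary endpoint analysis, also attaches the interval to the difference, "with the corresponding exact 95% Clopper Pearson confidence intervals (CIs) will be presented", and a redacted block follows there.

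No interval method for a difference of proportions is visible elsewhere. SAP 8.1 says only that descriptive statistics may carry 95% confidence intervals. The mRS responder analysis in SAP 10.1.1 gives the difference "with the corresponding 95% confidence intervals (CIs) will be presented for the defined time points", and recurrent stroke in SAP 10.2.1 has: "The difference of the proportions between the treatment groups with the corresponding 95% CIs will be presented". SAP 10.1.2 and 10.2.6 are worded alike. A chi-square test is named for some efficacy endpoints, but it is a test, not an interval, and is not tied to the primary endpoint.

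On status, SAP 10 states that "all statistical comparison between the treatment groups is not of confirmatory but of descriptive nature". On precedence, protocol 13 states: "The SAP will serve as a compliment to the protocol and supersedes it in case of differences".

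**The concern.** Clopper-Pearson inverts the tail probabilities of one binomial distribution. A difference of two independent proportions involves two binomials and a nuisance parameter, so the method has nothing to say about it. The sentence can be read in three ways:

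- Clopper-Pearson limits for each arm are shown beside the difference. This is the most natural reading, and it leaves the difference with no interval.
- The limits of one arm are subtracted from those of the other. This gives an interval, but not a 95% one.
- An exact two-sample interval is meant. Its test statistic is then unstated, and the choice of statistic matters a great deal.

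In a descriptive study the estimate and its interval are the result. Here the interval accompanies the primary safety comparison, and as visibly written its method would be settled by whoever programs the table.

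**Working it through.** The plan shows no figure to reproduce: the sample-size text is not visible and no expected rate for the primary endpoint is given. The check asks how far the candidate intervals differ.

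**Inputs.** About 200 subjects randomised 1:1 (SAP 4.1), taken as 100 treated per arm. The level is 95%, taken as two-sided. Event counts are illustrative and do not come from the documents.

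**Methods.**

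- *Clopper-Pearson, one arm:* the lower limit is the 0.025 quantile of Beta(x, n-x+1) and the upper limit is the 0.975 quantile of Beta(x+1, n-x). The lower limit is 0 when x = 0.
- *Arm limits subtracted:* (L1 - U2, U1 - L2).
- *Newcombe:* with Wilson limits (l, u) for each arm, the lower limit is d - sqrt[(p1-l1)^2 + (u2-p2)^2] and the upper limit is d + sqrt[(u1-p1)^2 + (p2-l2)^2].
- *Miettinen-Nurminen:* the values of the difference at which the score statistic, with restricted maximum likelihood variance multiplied by N/(N-1), equals ±1.96.
- *Exact unconditional:* two one-sided tests at 0.025, each p-value maximised over the nuisance rate. The tests order outcomes either by the score statistic or by the raw (unstandardized) difference.

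**Worked case, 5 vs 0 at 100 per arm.** Clopper-Pearson gives 1.64% to 11.28% and 0% to 3.62%. Subtracted: 1.64 - 3.62 = -1.98 and 11.28 - 0 = 11.28. The Wilson limits are 2.154% to 11.175% and 0% to 3.699%. The Newcombe lower limit is 5 - sqrt(2.846^2 + 3.699^2) = 5 - 4.667 = 0.33, and the upper limit is 5 + 6.175 = 11.18.

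| Method (5 vs 0) | 100 per arm | 90 per arm |
|---|---|---|
| Arm limits subtracted | -1.98% to 11.28% | -2.19% to 12.49% |
| Newcombe | 0.33% to 11.18% | 0.38% to 12.35% |
| Miettinen-Nurminen | 1.19% to 11.20% | 1.33% to 12.38% |
| Exact, score statistic | 0.90% to 11.31% | 1.00% to 12.56% |
| Exact, unstandardized | -9.33% to 19.18% | -9.57% to 20.50% |

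At 100 per arm the two exact intervals are 28.51 and 10.41 points wide, a ratio of 2.7. The 90-per-arm column is a sensitivity case, because the Safety population requires a dose and protocol 8.3 says: "Randomized but not treated subjects will not be replaced".

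**Sparse events, 100 per arm.**

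| Events | Subtracted | Newcombe | Width ratio |
|---|---|---|---|
| 0 vs 0 | -3.62% to 3.62% | -3.70% to 3.70% | 0.98 |
| 1 vs 0 | -3.60% to 5.45% | -2.79% to 5.45% | 1.10 |
| 2 vs 0 | -3.38% to 7.04% | -1.97% to 7.00% | 1.16 |
| 3 vs 0 | -3.00% to 8.52% | -1.19% to 8.45% | 1.19 |

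At 0 vs 0, Miettinen-Nurminen gives ±3.72%, exact score ±3.78% and exact unstandardized ±14.27%. A Wald interval collapses to 0 to 0.

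**Events in both arms.** At 5 vs 2: subtracted -5.40% to 11.04%, Newcombe -2.75% to 9.34%, Miettinen-Nurminen -2.64% to 9.46%.

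**Coverage of subtracted limits**, by full enumeration of both binomials at 100 per arm: 99.99% at true rates 2% and 2%, 99.8% at 5% and 2%, 99.7% at 10% and 5%. Over rates from 0.5% to 30% differing by at most 5 points, the lowest value found was 98.5%, at 4.13% vs 0.5%.

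**The case against.** The best defence is that the sentence is loosely worded rather than wrong. Read as Clopper-Pearson limits for each arm, it uses the method correctly, and what remains is an unnamed method for the difference, a gap shared with the efficacy endpoints. That reading is plausible, but the text attaches the limits to the difference in three places, and on the kinder reading the primary difference has no stated interval. The correction is the same.

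Events may also be very few. Protocol 5.3 reports that all adverse events in LT3001-103 were unrelated or unlikely related, that the one headache in LT3001-101 was only possibly related, and that all serious events in LT3001-201 were unrelated or unlikely related. The endpoint counts only probable or definite relation. With 0 to 3 vs 0 events, subtraction and Newcombe differ little. The 5 vs 0 case sits where the answer changes: at 4 vs 0 Newcombe still includes zero (-0.4% to 9.8%). The over-coverage also shrinks near zero, to 97.6% at true rates of 3.65% and 0%. All of this stands and limits the practical effect.

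No document names the unstandardized exact interval, so that contrast is hypothetical. It shows only why the word exact needs a statistic beside it.

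A method could also sit in redacted text or in the separate table shells. The point is therefore that no applicable method is visible, not that none exists. Hidden text would still leave the visible sentence wrong. Finally, arm counts and percentages are reported, so a reader could recompute an interval.

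**Conclusion.** The concern holds: the stated method does not apply to the quantity it is attached to, and no visible text supplies one that does. At 5 vs 0 events the choice decides whether the interval includes zero; the exact variants differ 2.7-fold in width; and subtracted limits cover at least 98.5%, not 95%, over the range examined. These sizes rest on 100 treated per arm and illustrative counts; at 90 per arm the pattern is the same. With very sparse events the choice between subtraction and Newcombe matters little. Because comparisons are descriptive, with no visible test, margin or decision rule on this interval, neither type I error nor sample size is affected. It should be fixed, since it concerns the primary endpoint's reported interval and the correction is simple.

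**What to change.** Before unblinding, replace the sentence in SAP 11.1, which governs where it differs from the protocol, with:

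> Exact 95% Clopper-Pearson CIs will be presented for the proportion in each treatment group. The difference in proportions (LT3001 minus placebo) will be presented with an exact unconditional 95% CI obtained by inverting two one-sided tests based on the score statistic.

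This keeps the plan's intention of an exact interval. Miettinen-Nurminen or Newcombe would cure the defect equally well. What is needed is one named two-sample method that gives limits with zero events. If it is exact, state the statistic and avoid the unstandardized version. Align protocol 13.4.1 and the synopsis at the next amendment.

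The cost is one sentence and one programming option, with no extra data. As the SAP is already Final v1.0, the change needs a version-controlled revision.

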11.2. Secondary safety endpoints

The occurrence of sICH and aICH [REDACTED] after the 1st IP will be assessed as part of the bleeding assessment.

A subject listing of bleeding assessment will be provided.

This document is confidential.

11.2.1. Occurrence of sICH [REDACTED] after the 1st IP

The number and percentage of subjects with sICH [REDACTED]

[REDACTED] after the 1st IP will be presented by treatment group and overall on the Safety population, and additionally within [REDACTED]

11.2.2. Occurrence of aICH [REDACTED] after the 1st IP

The number and percentage of subjects with aICH [REDACTED]

[REDACTED] after the 1st IP will be presented by treatment group and overall on the Safety population, and additionally within [REDACTED]

11.2.3. Occurrence of mortality due to any reason within 90 days after the 1st IP

The number and percentage of subjects who have died because of any reason within 90 days after the 1st IP will be presented by treatment group and overall for the Safety population [REDACTED]

11.2.4. Adverse Events

An AE is any symptom, physical sign, syndrome, or disease that either emerges during the study or, if present on or after the 1st IP administration [REDACTED], worsens during the study, regardless of the suspected cause of the event. AEs are defined as Treatment-emergent adverse events (TEAEs) in the SAP and TLFs.

An SAE is any untoward medical occurrence, in the view of either the Investigator or Sponsor, that:

- results in death,
- is life-threatening,
- results in inpatient hospitalization or prolongation of existing hospitalization,
- results in persistent or significant disability/incapacity, and/or
- is a congenital anomaly/birth defect

Other important medical events that may not be immediately life-threatening or result in death or hospitalization, based upon appropriate medical judgment, are considered SAEs if they are thought to jeopardize the subject and/or require medical or surgical intervention to prevent one of the outcomes defining an SAE.

This document is confidential.

Also, Related TEAE is an any event deemed possibly, probably or definitely related to treatment.

All AEs will be coded using the actual version of MedDRA dictionary to provide the system organ class (SOC) and preferred term (PT). Duration of the adverse event (AE) will be calculated and presented in days. Duration of the AE is defined as (AE end date – AE start date) + 1.

The number and percentage of subjects as well as number of events will be presented for TEAE summaries. An overall summary of TEAEs including the following categories will be presented:

- at least one TEAE
- at least one serious TEAE
- at least one related TEAE
- at least one TEAE leading to study drug withdrawal
- at least one TEAE with fatal outcome

A summary table of TEAEs by SOC and PT will be presented. Multiple instances of the TEAE in each SOC and multiple occurrences of the same PT are counted only once per subject. The denominator used for calculating the percentages will be the total number of subjects included in the safety population.

In addition, for each of the following, a summary of TEAEs will be produced at the subject level:

- Serious TEAEs by SOC and PT
- TEAEs by worst intensity by SOC, PT
- TEAEs by maximum relationship by SOC, PT
- TEAEs leading to study drug withdrawal

All AEs for each subject, including multiple occurrences of the same event, will be presented in full in a comprehensive listing sorted by subject number.

